# 6.6.2 Management of Severe Hypersensitivity Reactions and Flu-Like Symptoms

Symptoms of hypersensitivity may include impaired airway, decreased oxygen saturation (<92%), confusion, lethargy, hypotension, pale or clammy skin, and cyanosis. These symptoms may, if necessary, be managed with epinephrine and dexamethasone. Oxygen therapy should be administered as appropriate. Patients should be monitored per institutional standards.

# 6.7 Discontinuation of One Study Drug

Patients receiving combination therapy with both ipilimumab and nivolumab may experience a severe adverse event that is felt to be primarily attributable to only one of the study drugs (i.e. an infusion-related reaction during nivolumab or an irAE more commonly observed with ipilimumab, etc). If a patient experiences an AE that would result in study treatment discontinuation per protocol that is felt to be primarily related to a single study drug, the patient may continue receiving the other agent on protocol, if approved by the principal investigator.

## 6.8 Study-wide early stopping rules

Observation of >1 treatment-related grade 5 event would pause accrual and initiate a study-wide review.

Excessive toxicity will be defined as grade 4 AEs or grade 3 AEs lasting > 72 hours (excluding asymptomatic laboratory AEs). Observation of excessive toxicity in >3 patients would pause accrual and initiate a study-wide review.

## 7. ADVERSE EVENTS: LIST AND REPORTING REQUIREMENTS

Adverse event (AE) monitoring and reporting is a routine part of every clinical trial. The following list of reported and/or potential AEs (Section 7.1) and the characteristics of an observed AE (Section 7.2) will determine whether the event requires expedited reporting **in addition** to routine reporting.

# 7.1 Expected Toxicities

#### 7.1.1 Adverse Events List(s)

# 7.1.1.1 Ipilimumab

## Common (>20% incidence)

- Diarrhea, nausea
- Fatigue
- Immune-related adverse events including the following:
  - Dermatitis

# Occasional (4-20% incidence)

DF/HCC Protocol #: 21-204

Protocol version date: v8/06 September 2023

- Abnormal heartbeat
- Hearing loss
- Swelling and redness of the eye
- Pain
- Difficulty swallowing, eating
- Constipation, vomiting
- Weight loss, loss of appetite
- Fever
- Dehydration
- Pain or swelling of the joints
- Infusion reaction during or following a drug infusion
- Immune-related adverse events including the following:
  - o Pneumonitis
  - o Colitis
  - o Kidney problems, including nephritis and kidney failure requiring dialysis
  - o Myositis
  - Neuritis
  - Endocrine gland problems (especially the thyroid, pituitary and adrenal glands, and pancreas

# Rare (<3% incidence)

- Bleeding
- Bowel obstruction
- Fluid around heart
- Severe illness with multiorgan failure
- Swelling of the brain which may cause headache, blurred vision, stiff neck, and/or confusion
- Immune-related adverse events including the following:
  - o Hyperglycemia
  - o Myocarditis, including swelling and heart failure.
- Complications associated with stem cell transplant using donor stem cells

## 7.1.1.2 Nivoluamb

# Frequent (>10% incidence)

- Diarrhea
- Fatigue
- Itching
- Rash

# Occasional (1-10% incidence)

- Allergic reaction (hypersensitivity).
- Abdominal pain
- Increased alkaline phosphatase, aspartate aminotransferase, bilirubin or alanine aminotransferase.
- Increased amylase or lipase

DF/HCC Protocol #: 21-204

Protocol version date: v8/06 September 2023

- Chills
- Constipation
- Cough
- Increased blood level of creatinine
- Decreased appetite
- Dizziness
- Dry mouth
- Dry skin
- Fever
- Headache
- Hyperglycemia
- Colitis
- Mucositis
- Infusion reaction
- Loss of color (pigment) from areas of skin
- Pneumonitis
- Muscle and/or bone pain
- Nausea
- Hyponatremia
- Swelling, including face, arms, and legs
- Hypothyroidism or hyperthyroidism
- Neuropathy
- Vomiting

# Rare (0.1%-1% incidence)

- Hypophysitis
- Lung inflammation (bronchitis)
- Cranial nerve disorder, which may cause facial pain or twitching, dizziness, hearing loss, weakness, and/or paralysis.
- Dehydration
- Diabetes complications resulting in excessive blood acids
- Double Vision
- Dry eye
- Erythema Multiforme
- Hair loss
- Tachycardia or heart arrhythmias
- Hypertension
- Irregular heartbeat
- Hives
- Inflammation of the eye
- Nephritis
- Inflammation of the pancreas, causing pain in the upper abdomen.
- Inflammation of the pituitary gland, which may cause headaches, change in eyesight, few to no menstrual cycles (for women), increased thirst, and increased frequency passing urine.
- Gastritis

DF/HCC Protocol #: 21-204

Protocol version date: v8/06 September 2023

- Thyroiditis
- Hepatitis
- Joint pain or stiffness
- Low blood pressure
- Pemphigoid
- Pituitary gland function decreased
- Psoriasis
- Kidney failure
- Myositis (an infection of the muscle).
- Infection in the upper respiratory tract
- Vision blurred

# Very rare (< 0.1% incidence)

- Life-threatening allergic reaction
- Damage to the protective covering of the nerves in the brain and spinal cord
- Disease caused by the body's immune system attacking healthy organs
- Drug induced liver injury
- A disorder called Guillain-Barré syndrome in which the body's immune system attacks part of the peripheral nervous system.
- Inflammation of blood vessels that can lead to damage of different organs
- Inflammation of the brain, potentially life-threatening or fatal Inflammation of the heart muscle.
- Inflammation of the lining of the brain and spinal cord
- Lung infiltrates, associated with infection or inflammation
- A neurologic syndrome characterized by muscle weakness called myasthenic syndrome, including myasthenia gravis
- Polymyalgia rheumatic
- Rupture of the intestine/hole in the intestine
- Sarcoidosis
- Stevens Johnson syndrome or Toxic Epidermal Necrolysis
- A disorder of the lymph nodes called histiocytic necrotizing lymphadenitis or Kikuchi lymphadenitis

## 7.2 Adverse Event Characteristics

• CTCAE term (AE description) and grade: The descriptions and grading scales found in the revised NCI Common Terminology Criteria for Adverse Events (CTCAE) version 5.0 will be utilized for AE reporting. All appropriate treatment areas should have access to a copy of the CTCAE version 5.0. A copy of the CTCAE version 5.0 can be downloaded from the CTEP web site

http://ctep.cancer.gov/protocolDevelopment/electronic applications/ctc.htm.

## • For expedited reporting purposes only:

- AEs for the agent(s) that are listed above should be reported only if the adverse event varies in nature, intensity, or frequency from the expected toxicity information which is provided.

DF/HCC Protocol #: 21-204 Protocol version date: v8/06 September 2023

- Other AEs for the protocol that do not require expedited reporting are outlined in the next section (Expedited Adverse Event Reporting) under the sub-heading of Protocol-Specific Expedited Adverse Event Reporting Exclusions.

#### • **Attribution** of the AE:

- Definite The AE *is clearly related* to the study treatment.
- Probable The AE *is likely related* to the study treatment.
- Possible The AE *may be related* to the study treatment.
- Unlikely The AE *is doubtfully related* to the study treatment.
- Unrelated The AE *is clearly NOT related* to the study treatment.
- A serious adverse event (SAE) is an AE that meets any of the following criteria:
  - Results in death (i.e., the AE actually causes or leads to death)
  - Is life-threatening (i.e., the AE, in the view of the investigator, places the patient at immediate risk of death. It does not include an AE that, had it occurred in a more severe form, might have caused death.)
  - Requires or prolongs inpatient hospitalization
  - Results in persistent or significant disability/incapacity (i.e., the AE results in substantial disruption of the patient's ability to conduct normal life functions)
  - Results in a congenital anomaly/birth defect in a neonate/infant born to a mother exposed to ipilimumab and/or nivolumab
  - Important medical events that may not result in death, are not immediately life-threatening, or do not require hospitalization may be considered SAEs when, based on appropriate medical judgment, they may jeopardize the subject and may require medical or surgical intervention to prevent one of the outcomes listed in this definition. Examples of such events include allergic bronchospasm requiring intensive treatment in an emergency room or at home, blood dyscrasias or convulsions that do not result in inpatient hospitalization, or the development of drug dependency or drug abuse.

# 7.3 Adverse Event Reporting

- 7.3.1 In the event of an unanticipated problem or life-threatening complications treating investigators must immediately notify the PI.
- 7.3.2 Investigators **must** report to the PI any adverse event (AE) that occurs after the initial dose of study treatment, during treatment, or within 30 days of the last dose of treatment on the local institutional SAE form.

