#### 5. TREATMENT PLAN

## Figure 1 Trial Schema

Patients with R/R cHL who have previously failed a PD-1 mAb will be enrolled. For details regarding dosing, see section 5.1. Study therapy is expected to be administered on an outpatient basis. Patients will receive 4 doses of ipilimumab therapy dosed every 3 weeks (12 weeks), followed by a restaging PET/CT scan. Patients achieving an objective response to ipilimumab monotherapy will receive up to 8 doses of maintenance ipilimumab dosed every 12 weeks (96 weeks), for a total of 108 weeks of study therapy. Patients with SD or PD following ipilimumab monotherapy (who are clinically stable) will receive 4 cycles of combination ipilimumab and nivolumab therapy dosed every 3 weeks (12 weeks), followed by up to 7 doses of maintenance ipilimumab dosed every 12 weeks (84 weeks), for a total of up to 108 weeks of study therapy. Patients who have progressive disease after fewer than 4 cycles of ipilimumab are eligible to proceed to combination therapy with nivolumab and ipilimumab if they are clinically stable. Therapy will be stopped sooner for unacceptable toxicity, patient withdrawal, disease progression, physician decision, or death. Patients achieving a complete response for ≥ 6 months

can elect to stop study therapy.

Patients will be evaluated with PET/CT scans at baseline and again after 4 doses of ipilimumab monotherapy (week 12) (or earlier if there is clinical concern for progression). Among ipilimumab responders, restaging scans will occur prior to ipilimumab maintenance cycle 2 (week 24), cycle 3 (week 36), cycle 5 (week 60), and cycle 7 (week 84). Among ipilimumab non-responders, restaging scans will occur after 4 cycles of ipilimumab + nivolumab combination therapy (week 24) and prior to ipilimumab maintenance cycle 2 (week 36), cycle 4 (week 60), and cycle 6 (week 84). The end-of-treatment assessment will occur 4-12 weeks after the last doses of study therapy (i.e. weeks 112-120 for patients who complete all planned study therapy). Afterwards, patients will be re-imaged every 24 weeks. Patients in CR at any time point may have CT imaging only at subsequent time points.

Toxicity will be continuously monitored and recorded using CTCAE 5 criteria, up to 30 days following the last dose of the study treatment or until resolution of toxicity to grade 1 or baseline, whichever occurs last.

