### 5.4 General Concomitant Medication and Supportive Care Guidelines

Protocol version date: v8/06 September 2023

Medications or vaccinations specifically prohibited in the exclusion criteria are also not allowed during the active treatment period, except for administration of inactivated vaccines (for example, inactivated influenza vaccine). If there is a clinical indication for one of these or other medications or vaccinations specifically prohibited during the trial, permanent discontinuation from study therapy may be required. The Investigator should consult with the Principal investigator about individual cases. The final decision on any supportive therapy or vaccination rests with the Investigator and/or the patient's primary physician. However, the decision to continue the patient on study therapy or medication/vaccination schedule requires the mutual agreement of the Investigator, the Principal investigator, and the patient. Prior/concomitant treatment considered necessary for the patient's well-being may be given at discretion of the treating physician.

Concomitant medications and treatments, including herbal supplements, will be recorded from 28 days prior to the start of study treatment and up to 90 days after the last dose of study treatment (at Days 30, 60, and 90 post-treatment +3 days). All concomitant medications and Non-Drug Supportive Interventions should be recorded in the CRF including supportive care drugs (eg, antiemetic treatment and prophylaxis), and the drugs used to treat adverse events or chronic diseases, and non-drug supportive interventions (eg, transfusions).

Medications intended solely for supportive care (ie, antiemetics, analgesics, megestrol acetate for anorexia) are allowed.

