# 7.4 Reporting to Bristol-Myers Squibb

Bristol-Myers Squibb (BMS) will also be informed of any serious adverse event (SAE) that occurs after the initial dose of study treatment, during treatment, or within 30 days of the last dose of treatment. Any SAE occurring after the reporting period must be promptly reported if a causal relationship in the investigational drug is suspected. Participant or partner pregnancy while on treatment or within 30 days of the last dose of treatment is also required to be reported to BMS via expedited reporting procedures.

Within 24 hours of first awareness of the event (immediately if the event is fatal or life-threatening), the study team will report to BMS by email ([contact]) any Serious Adverse Event ("SAE," as defined below) for which reporting is required under this provision (as described below). Such SAEs are to be reported for study subjects or individuals otherwise exposed to study drugs as described below. The study teams should report SAEs as soon as they are determined to meet the definition, even if complete information is not yet available.

SAEs to BMS will be reported on a SAE report form supplied by BMS and sent to the Sponsor-Investigator to review and report to [contact] on behalf of the reporting external site. Submissions should be made within 24 hours of the site's knowledge of the event.

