# 7.4.4 SAE Reporting Period

The SAEs that are subject to this reporting provision are those that occur from after the first dose of study medication(s) through 30 calendar days after the last administration of the study medication(s). In addition, if a Sponsor-Investigator becomes aware of an SAE occurring within 30 days of last dose of study medication the Sponsor-Investigator should report that SAE to BMS if the Sponsor-Investigator suspects a causal relationship between the study drug and the SAE. In addition, if the investigator determines that an SAE is associated with study procedures, the investigator must record this causal relationship in the source documents.

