# 10.3 Required at Progression or Treatment Discontinuation and Follow-Up

- Medication review, physical exam, vital signs, ECOG performance status (see Appendix A)
- Toxicity assessment
- CBC with manual differential, blood chemistries including complete metabolic panel, phosphorus, magnesium, uric acid, LDH, TSH, creatinine kinase, lipase, triglycerides. Urine studies to include a urine dipstick for blood and protein and if positive a microscopic urinalysis and 24-hour urine collection (for protein).
- Peripheral blood sample for biomarker studies at the time of progression (if feasible)
- Core-needle tumor biopsy at the time of progression (optional)
- Tumor restaging will be performed for patients in long-term follow-up who remain in remission. Patients who progress or receive other therapy for their lymphoma (for example, consolidation with transplantation or an alternative treatment) will only be followed for relapse and survival). Surveillance imaging will consist of PET/CT scans (including neck, chest, abdomen/pelvis) every 24 weeks for up to 2 years after initiation of study therapy.

DF/HCC Protocol #: 21-204 Protocol version date: v8/06 September 2023

• Patients in remission will be followed every 3 months for 2 years, then every 6 months for 3 years. Patients who progress or receive other therapy (for example consolidation with transplantation or an alternative treatment) will only be followed for relapse and survival.

• After 5 years of active follow up (for patients who remain in remission and do not receive additional treatment), patients will be followed only for relapse and survival with follow up by phone call with the patient or the local physician every 6 months for up to 5 years.

	Table 7 - Study Calendar											
	Baseline	Сус	ele 1ª	Cycle 2	Cycle 3	Cycle 4	Re- induction cycles 1-4 b	Maintenance Cycles c		ЕОТ	Follow- Up d, j	EDC Timepoints
	Day-28 to Day 0	Day 1	Day 14- 21	Day 1	Day 1	Day 1	Day 1	Day 1	Day 43	4-12 weeks from last study treatment		
					±3	days				± 7 days	±2 weeks	
Ipilimumab		X		X	X	X	(X)	X				Day 1 of induction and re-induction cycles and each maintenance cycle
Nivolumab							(X)					Day 1 of re- induction cycles
Informed consent	X											N/A
Demographics	X											Baseline
Medical history	X											Baseline
B-HCG e	X	X		X	X	X						Baseline
Urinalysis Hepatitis B and	X											Baseline
C serologies f	X											Baseline

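### New adverse events are collected for 30 days after the last dose although later contacts already exist, and the safety analysis does not say whether later events count

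*Combined protocol and SAP*

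**What the plan says.** **The 30-day window.** Section 7.3.2 requires adverse events to be reported to the principal investigator from the first dose, during treatment, or "within 30 days of the last dose of treatment on the local institutional SAE form". Section 5 (text under Figure 1) has toxicity monitored and recorded "up to 30 days following the last dose of the study treatment or until resolution of toxicity to grade 1 or baseline, whichever occurs last". Section 7.4.4 runs the SAE period "through 30 calendar days after the last administration of the study medication(s").

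**Contacts after day 30.** Section 5.4 requires concomitant medication to be recorded "up to 90 days after the last dose of study treatment (at Days 30, 60, and 90 post-treatment +3 days"). Section 10.2 schedules a day-43 visit in each maintenance cycle. Section 5 and Table 7 place the end-of-treatment visit 4 to 12 weeks after the last dose, and 10.3 ("Required at Progression or Treatment Discontinuation and Follow-Up") lists a toxicity assessment without a look-back period.

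**Late serious events.** Section 7.4 states: "Any SAE occurring after the reporting period must be promptly reported if a causal relationship in the investigational drug is suspected". The matching sentence in 7.4.4 instead refers to a sponsor-investigator who "becomes aware of an SAE occurring within 30 days of last dose of study medication". Section 7.7 requires all adverse events to go onto the toxicity case report forms, including those already sent through expedited channels.

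**Analysis.** Section 13.4 defines three safety rates: grade 3 or higher regardless of attribution, grade 3 or higher at least possibly related, and grade 2 or higher at least probably related. Section 13.5.1 makes every treated patient evaluable from the first treatment. Neither section gives an end to the window.

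**The concern.** Both drugs act through the immune system and clear slowly, so a first immune event some weeks after the last dose is plausible. Under 5.4, a steroid started at day 60 would be recorded as a concomitant medication, but nothing clearly requires the event that prompted it to be recorded as an adverse event.

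Ascertainment also depends on whether a patient is still being dosed. On maintenance, an event at day 60 of an 84-day cycle is on treatment and counts. The same event 60 days after a final induction, re-induction or maintenance dose is outside the 30-day limit.

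With 13 patients, each safety rate rests on a handful of events. If the cut-off is not fixed in advance, whoever prepares the tables must decide about late events after seeing them.

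**Working it through.** **1. Is there a plan figure to reproduce?** None bears on this point. The only design calculation is in 13.3: reject if 4 or more of 13 respond, with null ORR 10% and alternative 40%. Exact binomial tails give a one-sided type I error of 0.0342 and power of 0.831, which match the stated 0.034 and 0.83. The adverse-event window affects neither.

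**2. What happens to an event that starts on days 31–90 after the last dose?**

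| Route | Covers it? |
|---|---|
| 7.3.2 | No; ends at day 30 |
| Section 5, extension to resolution | Follows toxicities already open; does not clearly admit new ones |
| 5.7, follow-up after removal for an adverse event | Only the event that led to removal |
| 7.4, late SAEs | Yes, if serious and suspected to be related; 7.4.4 is worded differently |
| 7.7, routine reporting | States no cut-off, but schedules no enquiry |
| 10.3 and end-of-treatment visit | May find it; timing varies from day 28 to day 84, with no look-back or counting rule |
| Follow-up visits (10.3, Table 7 note d) | Three-monthly for patients in remission; patients who progress or start other therapy are followed only for relapse and survival |
| 5.4, days 30, 60 and 90 | Contact exists for medication only |

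What remains uncovered is a new, non-serious event after day 30 in a patient who has stopped.

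The end-of-treatment visit may come later still for patients who complete therapy. Section 5 sets it at weeks 112–120. Maintenance cycle 7 is at week 84 for responders, so dose 8 falls at 84 + 12 = week 96. The visit is then 112 − 96 = 16 to 120 − 96 = 24 weeks after that dose.

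**3. Drug remaining after the last dose.** Fraction = 0.5^(days / half-life), assuming simple exponential decline. Half-lives: ipilimumab 15.4 days (2.2.3); nivolumab 25 days (2.3.3) or 17–25 days (8.2.1).

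| | Day 30 | Day 90 |
|---|---|---|
| Ipilimumab, 15.4 d | 0.5^(30/15.4) = 25.9% | 0.5^(90/15.4) = 1.7% |
| Nivolumab, 25 d | 0.5^(30/25) = 43.5% | 0.5^(90/25) = 8.2% |
| Nivolumab, 17 d | 0.5^(30/17) = 29.4% | 0.5^(90/17) = 2.5% |

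This bears on plausibility. It is not an event rate.

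**4. Effect of one missed patient.** 1/13 = 7.7 points. For example, 5/13 = 38.5% (exact 95% CI 13.9–68.4) becomes 4/13 = 30.8% (9.1–61.4).

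**5. Illustration under assumptions.** The documents give neither the true toxicity rate *t* in this trial nor the share *f* of events that start on days 31–90. Assume *t* = 30–50% and *f* = 5–30%.
- Expected missed = 13 × *t* × *f*: from 13 × 0.30 × 0.05 = 0.2 to 13 × 0.50 × 0.30 = 1.95 patients.
- Chance of missing at least one = 1 − (1 − *t f*)^13: from 1 − 0.985^13 = 18% to 1 − 0.85^13 = 88%.

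For these assumed values the figures are upper bounds. They treat every patient as having stopped and ignore every capture route in step 2.

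**The case against.** The best reply is that collection does not simply end at day 30. Section 7.3.2 concerns notifying the principal investigator on the SAE form. Routine collection falls under 7.7, which has no cut-off. Section 5 follows open toxicities to resolution, and the end-of-treatment visit can be as late as week 12. All of that stands. But Section 5 puts the same 30 days on recording toxicity, and none of these routes requires a site to ask about new events at days 60 and 90.

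Three stronger readings are tempting, and the documents do not support them.

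- *Late events drop out of the safety rates.* A reader might infer this from 7.3.2. Sections 13.4 and 13.5.1 state no cut-off, so exclusion is possible but not prescribed.
- *Late SAEs reach the supplier but not the analysis.* Section 7.7 sends events reported through expedited channels into routine data as well.
- *The comparison of maintenance with combination patients is biased.* No such test is planned. Section 1.3 asks for rates within each population, 13.3 calls the re-induction analysis descriptive, and combination patients go on to maintenance, so the groups overlap. The 30-day limit also applies after the last maintenance dose. The contrast is between patients who have stopped and patients still on treatment.

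Two further points hold. The day 30, 60 and 90 contacts appear only in 5.4 and have no columns of their own in Table 7, so they need to be written in. And a 90-day tail would not equalise total observation time, because exposure can run from one dose to 108 weeks.

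**Conclusion.** The point holds as a gap in ascertainment and a missing analysis rule. New, non-serious events after day 30 in patients who have stopped lie outside the window in Section 5 and 7.3.2, although 5.4 already provides for contact at days 60 and 90. The statistical section leaves their status open.

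The number of events at stake cannot be derived from the documents. What can be said is that one patient moves a rate by 7.7 points, and that a material fraction of both drugs remains at day 30 under exponential decline at the stated half-lives. The primary endpoint, type I error and power are untouched. This is an inexpensive improvement to a secondary safety endpoint. It does not show that the planned rates are wrong.

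**What to change.** - **Collection (Section 5, 7.3.2).** Collect all grade 2 or higher adverse events, with attribution recorded, through day 90 after the last dose, or until new anticancer therapy if earlier. Use the 5.4 contacts. An extension limited to related events would give the rate that ignores attribution two different windows.
- **Calendar (Table 7, 10.3).** Add the day 30, 60 and 90 contacts, and state that they also apply to patients who stop for progression.
- **Analysis (13.4, 13.5.1).** Use this one window for all three safety rates, and show a 30-day table alongside for comparison with other trials.
- **Serious events.** Reconcile 7.4 with 7.4.4 on SAEs after day 30.

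**Cost.** Slightly more data entry, at contacts that 5.4 already requires. The 90-day rates may look less favourable than 30-day rates, and some unrelated events will be added, which is why attribution and the 30-day table are needed. Sample size and the primary analysis do not change.
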